Study Protocol

Title: Prevalence of Carotid Web in Youth Assessed by Duplex Sonography: a Cross-Sectional Study

Short Title: Carotid Web in Youth

Acronym: CaWY Study

ID: G25-498516

Version: 1.4

Date: October 20, 2025

Authors: [name] [name], M.D., Ph.D.

[name]., Ph.D.

[name]., Ph.D.

Affiliation: Center for Health Research, Faculty of Medicine, University of Ostrava, Ostrava, Czech Republic

1) Background and Rationale

A carotid web (CaW) is a shelf-like, thin, triangular endoluminal projection—typically arising from the posterior wall of the internal carotid artery (ICA) bulb—considered by many to be an intimal variant of fibromuscular dysplasia and associated with embolic ischemic stroke in otherwise low-risk, younger patients. Although CT angiography (CTA) is most frequently used to diagnose CaW, characteristic appearances are detectable by carotid duplex ultrasound (DUS) on longitudinal B-mode with supportive Doppler findings; microflow/superb microvascular imaging can improve conspicuity. Population prevalence in the general young adult population is unknown; most estimates come from stroke cohorts ($\approx 2\%$ among symptomatic populations; higher within cryptogenic stroke subsets), so a dedicated, population-based sonographic study is needed.

2) Objectives and Hypotheses

Primary objective: Estimate point prevalence of carotid web in a general young adult population aged 15–25 years using duplex sonography.

Secondary objectives:

- Describe CaW laterality and morphology (web thickness, length, and projection angle) on ultrasound.
- Estimate prevalence of concomitant ICA/CCA atherosclerotic change or stenosis.
- Assess inter-observer agreement for CaW detection on DUS.
- In an adjudicated subset, compare DUS-suspected CaW with CTA (optional validation).

Hypothesis: Carotid web is present in 2 % of the general 15–25-year population (two-sided).

(This is a planning assumption; true prevalence may be lower/higher. Literature in symptomatic cohorts ranges roughly 2%, higher in cryptogenic stroke; general-population data are lacking.)

3) Study Design

Cross-sectional, multi-center, population-based sonographic survey with blinded central image adjudication, reported per STROBE guidelines for cross-sectional studies.

4) Study Population

Inclusion criteria

- Age 15 – 25 years at enrollment.
- Able to provide informed consent.

Exclusion criteria (for primary analysis; still recorded if present):

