- Prior carotid endarterectomy/stenting, neck irradiation, or known vasculopathy with non-web lesions that preclude assessment.
- Inadequate acoustic window despite optimization (these participants contribute to feasibility metrics, not prevalence numerator/denominator).

Setting & sampling frame

- Community-based recruitment (secondary schools / universities).

- Stratified cluster sampling by sex, age bands (15-17, 18–21, 22–25), and recruitment site to approximate the underlying population.

5) Sample Size

Assumptions

- Expected prevalence $p=0.02$ (2%)
- Desired absolute precision $d=0.01$ ($\pm 1\%$)
- Confidence level 95% $\rightarrow Z=1.96$

Formula

$$n = \frac{Z^2 p(1-p)}{d^2} = \frac{1.96^2 \times 0.02 \times 0.98}{0.01^2} = 752.95$$

$$\frac{1.96^2 \times 0.02 \times 0.98}{0.01^2} = 752.95$$

Required minimum sample size: 753 participants (round up) plus 10% for non-diagnostic/poor-quality scans and no-shows, i.e. **totally 829 participants is needed to screen.**

6) Ultrasound Acquisition Protocol

Equipment & presets

- High-end ultrasound suplex machine Canon Aplio a-series with B-mode, color/power Doppler, spectral Doppler, and microflow/superb microvascular imaging. High-frequency linear transducer PLT-1005BT (5–14 MHz).
- Patient supine, slight neck extension/contralateral head rotation; optimize for the carotid bulb/ICA origin.

Scanning sequence (bilateral)

1. **B-mode:** transverse sweep from distal CCA through bulb into proximal ICA and ECA; then longitudinal (anterolateral, lateral, posterolateral windows).
2. **Color Doppler:** at low PRF to visualize flow separation/recirculation; adjust wall filter and gain to avoid overwriting thin intraluminal structures.
3. **Spectral Doppler:** with angle correction $\leq 60^\circ$, sample volume 1.5–2.0 mm; measure PSV and EDV in standard segments (distal CCA, bulb, proximal ICA).

4. **Microflow imaging:** focused on the posterolateral bulb to delineate thin shelf/membrane and adjacent flow.

Image storage

- Mandatory cine loops (≥ 3 cardiac cycles) in longitudinal and transverse of the bulb/ICA origin, plus still frames with and without color, and spectral Doppler waveforms with angle annotation ((same as in protocol of ANTIQUE study).
- Label side and projection; record machine make/model, probe, presets.

7) Sonographic Definition of Carotid Web

Definite carotid web:

Inclusion criteria:

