- **Vascular risk factors:** smoking status, BP at visit, lipid profile if available, personal history of stroke/TIA/migraine, OCP use (females), recreational drugs, connective tissue disease/FMD history.
- **Ultrasound fields:** laterality; CaW category (absent/possible/probable), web dimensions (length, thickness, projection angle—estimate), distance from flow divider, presence of superimposed thrombus, plaque descriptors, standard velocities (CCA, bulb, ICA), ICA/CCA PSV ratio, EDV.
- **Imaging quality scores** and reasons for non-diagnostic studies.

10) Validation Substudy

- Participants with definite or possible CaW on DUS plus 1:2 matched DUS-negative controls (matched by age/sex/site) will invited for CTA within 4 weeks to evaluate concordance (index test: DUS; reference standard: CTA with thin-slice oblique sagittal reconstructions). Outcome: sensitivity/specificity and positive predictive value of DUS criteria. (CTA descriptions of CaW as thin, shelf-like posterior bulb defects guide the reference call.)

11) Outcomes

- **Primary:** Point prevalence of **probable CaW** (participants with ≥ 1 carotid web / all with diagnostic scans), with 95% CI adjusted for sampling design.
- **Secondary:**
 - Prevalence including **possible + probable** (sensitivity analysis).
 - Distribution by side (left/right/bilateral).
 - Association between CaW and sex, smoking, BP, OCP use (exploratory).
 - Inter-observer agreement metrics.
 - In validation substudy: DUS diagnostic accuracy vs CTA.

12) Statistical Analysis Plan

- **Weighting:** Apply sampling weights for cluster/strata to estimate population prevalence; robust SEs (Taylor linearization) or survey-design GLMs.
- **Descriptives:** Means/SDs or medians/IQRs; counts/% with 95% CIs.
- **Primary analysis:** Weighted prevalence and **exact (Clopper–Pearson) or Wilson** CIs for rare events; compare strata with Rao–Scott χ^2 .
- **Regression (exploratory):** Survey-weighted Poisson (log link, robust variance) for prevalence ratios of CaW vs candidate covariates.
- **Reliability:** Cohen’s κ with 95% CI (categorical), ICC(2,1) for continuous measures.
- **Missing data:** Report flow; use complete-case for primary prevalence; multiple imputation for covariate analyses if $>5\%$ missing.

- **Sensitivity analyses:** (i) include **possible** CaW as positive; (ii) restrict to scans with top quality scores; (iii) per-reader estimates.

13) Bias Minimization & Quality Control

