- Pre-specified imaging protocol; machine presets harmonized across sites.
- Central training and periodic re-calibration; quarterly site audits of randomly selected studies.
- Consecutive sampling within clusters to reduce selection bias; track response rates.
- Maintain blinding; lock image sets before adjudication.

14) Ethics and Safety

- Minimal-risk imaging study; no ionizing radiation in the primary protocol.
- Informed consent; separate consent for optional CTA.
- Participants with **incidental significant carotid stenosis** or suspected thrombus receive counseling and referral per local care pathways.
- Data privacy per GDPR; coded IDs; secure storage.

15) Feasibility & Timeline

- **July-December 2025:** Finalize SOPs, train sonographers, pilot 50 scans to confirm criteria and quality metrics.
- **January 2026 – June 2026:** Enrollment and scanning.
- **May – June 2026:** Central reads and adjudication.
- **July – December 2026:** Analysis, manuscript preparation.

16) Case Report Forms (CRFs) — Core Fields (summary)

- **CRF-1 (Eligibility & Consent).**
- **CRF-2 (Demographics/Risk).**
- **CRF-3 (Ultrasound Acquisition):** device, probe, settings, windows obtained, quality.

- **CRF-4 (Ultrasound Findings):** CaW category; measurements; Doppler velocities; plaque; stenosis category; images saved (IDs).
- **CRF-5 (Adjudication):** reader A/B calls; consensus; κ .
- **CRF-6 (Validation Substudy):** CTA done (Y/N), CTA result (CaW Y/N), discordance reason.

17) Reporting

- Report per **STROBE**; include gallery of representative DUS images (longitudinal shelf-like lesion, transverse membrane, microflow swirl) and a flow diagram. Explicitly discuss limitations: web detection is operator-dependent; ultrasound criteria are less standardized than CTA; very low prevalence may limit precision without large samples.

Key References (for protocol justification)

1. **Fontaine L, et al.** *Ultrasound characteristics of carotid web*. J Neuroimaging. 2022. Describes B-mode/Doppler appearances; microflow imaging improves detection. ([PMC](#), [PubMed](#))
2. **Chen H, et al.** *Carotid webs: pathophysiology, diagnostic approaches, and management*. J NeuroIntervent Surg. 2024. Overview; ultrasound visualization best in longitudinal B-mode. ([jn.is.bmj.com](#))
3. **Radiopaedia (review).** *Carotid web*. Emphasizes shelf-like defect at posterior ICA bulb and CTA reference standard. ([Radiopaedia](#))

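### The stated target is all 15–25-year-olds, but the only stated frame is schools and universities with consecutive intake, so the planned weights are not design weights and cannot give general-population prevalence

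*Protocol*

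**What the plan says.** - **Target (Protocol section 2, primary objective):** "Estimate point prevalence of carotid web in a general young adult population aged 15–25 years using duplex sonography".
- **Design label (section 3):** "Cross-sectional, multi-center, population-based sonographic survey with blinded central image adjudication".
- **Frame (section 4, setting and sampling frame):** "Community-based recruitment (secondary schools / universities"). No other route is named anywhere. The eligibility criteria do not require a participant to be a student; the restriction comes only from the frame.
- **Sampling design (section 4):** "Stratified cluster sampling by sex, age bands (15-17, 18–21, 22–25), and recruitment site to approximate the underlying population".
- **Intake inside clusters (section 13):** "Consecutive sampling within clusters to reduce selection bias; track response rates".
- **Weighting (section 12):** "Apply sampling weights for cluster/strata to estimate population prevalence; robust SEs (Taylor linearization) or survey-design GLMs". Section 11 attaches a design-adjusted 95% interval to the primary outcome.
- **Limitations (section 17):** the listed items are operator dependence, ultrasound criteria that are less standardised than those for CTA, and poor precision at very low prevalence. Coverage of the frame and the way participants are selected are not among them.

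**The concern.** Section 1 justifies the study by the lack of a general-population figure, since existing estimates come mostly from stroke cohorts. The value of the result therefore depends on whom the sample represents.

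Two features of the stated design stand in the way. First, the frame leaves out anyone aged 15–25 who is in neither secondary school nor university. The gap is probably widest in the 22–25 band, which section 4 makes a stratum but which can in practice be filled almost only through universities. Second, a sampling weight in the survey sense is the inverse of a known inclusion probability. Consecutive intake is a non-probability method, and the protocol states neither selection probabilities nor a random draw of clusters.

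At stake is the label on the headline number. A prevalence among students would be reported as one for the whole age group, with an interval that looks design-based. Taylor linearization and Rao–Scott tests allow for clustering in the variance. They do not correct for people who had no chance of being sampled.

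**Working it through.** **1. The plan's own figure.** Inputs from section 5: p = 0.02, d = 0.01, Z = 1.96.

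n = Z²p(1−p)/d² = 1.96² × 0.02 × 0.98 / 0.01² = 752.95, rounded up to 753. With the allowance, 753 × 1.10 = 828.3, rounded up to 829. Both stated figures reproduce and are not in dispute here. The planned ±1 percentage point serves below as the yardstick.

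**2. What the sections jointly imply.**

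| Step | Stated in | Consequence |
|---|---|---|
| Target is everyone aged 15–25 | 2, 3 | Each such person needs a non-zero chance of selection |
| Frame is schools and universities | 4 | Non-students have zero chance |
| Strata are sex, age band, site | 4 | Weights can rebalance these among students only |
| Consecutive intake inside clusters | 13 | No stated inclusion probability |
| Weights give population prevalence | 12 | Needs both properties that the preceding rows lack |

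**3. Size of the coverage error.** Let u be the share of the age group outside education and r the ratio of prevalence outside to prevalence inside. With 2% inside the frame:

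population prevalence = (1 − u) × 2% + u × r × 2%

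error = 2% − population prevalence = u × (1 − r) × 2%

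The documents give neither u nor r, so both are assumptions. Population prevalence is then:

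| u | r = 0.5 | r = 1 | r = 1.5 |
|---|---|---|---|
| 10% | 1.9% | 2.0% | 2.1% |
| 20% | 1.8% | 2.0% | 2.2% |
| 30% | 1.7% | 2.0% | 2.3% |
| 40% | 1.6% | 2.0% | 2.4% |

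The error runs from 0 to 0.4 percentage points in either direction. The largest value is 0.4/1.0 = 40% of the planned half-width and occurs only at the extreme corners (u = 40% with r = 0.5 or 1.5). At r = 1 it is zero for every u. Wider assumptions widen it: u = 50% with r = 2 gives 3.0%, an error of 1.0 point. Nothing in the protocol favours one row or column over another.

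**The case against.** The strongest defence is that section 4 does specify stratified cluster sampling and that the consecutive step applies only inside clusters. Weights for sex, age band and site can be formed without individual selection probabilities, by post-stratifying to known totals. If every eligible member of a cluster is approached, inclusion within that cluster is certain apart from non-response, and section 13 plans to track response. How weights are built is commonly left to the statistical analysis plan, which is not shown.

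Much of this stands. A reader might infer that the weights have no basis at all; the documents do not support that. What they support is narrower: such weights would be a model-based adjustment and would still leave out non-students. The frame and the intake method are fixed in the protocol, and a later analysis plan cannot recover people who were never sampled.

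A reader might also infer that early participants are volunteers enriched for symptoms or family history. The protocol says nothing of the kind. Consecutive intake ordinarily limits recruiter discretion, so compared with convenience selection the section 13 statement is fair. It does not claim representativeness in so many words; it simply does not supply what section 12 needs. Section 9 also collects personal history of stroke, TIA, migraine and connective tissue disease, so enrichment of that kind could be examined.

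The parenthesis in section 4 could be read as giving examples only. Even so, no route to non-students is stated.

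**Conclusion.** The point holds as a mismatch between the claimed target population and the stated frame and intake. The design described can estimate prevalence among students of the type sampled. It cannot, through the section 12 weights, deliver prevalence for all people aged 15–25, and those weights should not be presented as inverse selection probabilities.

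The size and direction of the bias are unknown. The range of 0 to 0.4 percentage points around 2% rests wholly on the assumed 10–40% outside education and the assumed ratios of 0.5–1.5. It is zero if carotid web is unrelated to being in education, and the documents do not address that relation. It would therefore be wrong to conclude that the estimate will be materially biased, or that the study loses its use. The sample-size arithmetic is unaffected. The change should be made, since the headline claim goes beyond the design and the section 17 limitations do not say so.

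**What to change.** - **Sections 2, 3 and 11:** restate the target population as students aged 15–25 at secondary schools and universities of the type sampled. Alternatively, keep the general-population target and add a recruitment route for people outside education.
- **Section 12:** describe the weights as post-stratification to the age × sex × site totals of that student population, using enrolment counts from the sites and the response rates already to be tracked. Provide for merging sparse cells: at 2% prevalence, 753 participants yield about 0.02 × 753 = 15 cases.
- **Section 13:** confine the statement to what consecutive intake does, namely limit discretion in whom recruiters approach, so that it cannot be read as making the sample representative.
- **Section 17:** add incomplete frame coverage and non-probability selection to the limitations.

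A random draw from class or faculty rosters is optional where sites can supply lists. It would give selection probabilities within clusters, but it means obtaining personal data from several institutions under GDPR during a January–June 2026 enrolment period, and non-response would remain. It would not reach non-students either.

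The cost of the main fix is protocol wording plus a request to each site for enrolment counts. The downside is a narrower stated target population. Adding a non-student route would cost more in recruitment, but is the option that keeps the general-population aim.
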